2.3. Definition of abbreviations

No	Abbreviations	Content
1	CABG	Coronary Artery Bypass Graft Surgery (Coronary Artery Bypass Grafting)
2	CTO	Chronic total occlusion (Chronic Total Occlusion)
3	eGFR	Estimated glomerular filtration rate (Estimated Glomerular Filtration Rate)
4	LAD	Left anterior descending artery (Left Anterior Descending Artery).
5	LCX	Left circumflex artery (Left Circumflex Artery)
6	LMT	Left main coronary artery (Left Main Trunk)
7	LVEF	Left ventricular ejection fraction (Left Ventricular Ejection Fraction).
8	PCI	Coronary Angioplasty (Percutaneous Coronary Intervention)
9	POBA	Percutaneous balloon-angioplasty (Plain Old Balloon Angioplasty).
10	Q1	First quartile
11	Q3	Third quartile
12	RCA	Right coronary artery (Right Coronary Artery).
13	SVG	Saphenous vein graft (Saphenous Vein Graft).
14	TLR	Target lesion revascularization (Target Lesion Revascularization).
15	TVR	Target vessel revascularization (Target Vessel Revascularization)

3. Method of analysis

3.1. Statistical analysis environment

Statistical analysis software: SAS Institute Inc., Windows version SAS version 9.4 or later

3.2. Calculation method of various items, etc.

Items	Calculation method, etc.
Summary statistics (consecutive numbers)	Mean, standard deviation, number of specimens, median, Q1, Q3, minimum, maximum and 95% confidence interval of the mean will be calculated. Number of Samples: Displayed as an integer Mean, standard deviation, median, Q1, Q3: displayed to one order of magnitude below the data of interest Minimum and Maximum Values Shown at the Same Digit as the Data Subject
Confidence interval of the mean	Confidence intervals based on t distributions are calculated. $CI = \bar{x} \pm t_{(1-\alpha/2;n-1)} \frac{s}{\sqrt{n}}$

Items	Calculation method, etc.
Summary statistics (incidence)	
Incidence rates (%), number of events (molecules), number of populations analyzed (denominators) and 95% confidence intervals of frequencies are calculated. However, cases in which the relevant variable is a missing value are also included in the population of the incidence calculation.
 
4.3 Population numbers for antiplatelet therapy and 4.4 adverse events are specified as follows.
 
4.3 Antiplatelet therapy
 
Newly enrolled patients will be included.
 
Pre-procedure: Case of stenting
 
Procedure Day to Discharge Day: Stenting Cases
 
Procedural Day ~ 8 Months Observation Day: 8 Months Analyzed by Case Time Point of Stenting
 
Procedural Day-1 Year Observation Day: 1 Year Analyzed by Time Point of Stent Implantation
 
Procedural Day ~ 2 Years Observation Day: 2 Years Analyzed by Time Point of Stent Implantation
 
Procedural Day ~ 3 Years Observation Day: 3 Years Analyzed by Time Point of Stent Implantation
 
Procedural Day ~ 4 Years Observation Day: 4 Years Analysis Population by Time Point of Stent Implantation
 
Procedural Day ~ 5 Years Observation Day: 5 Years Analysis Population by Time Point of Stent Implantation
 
4.4 Adverse Events
 
Newly enrolled patients will be included.
 
Procedural Day + 3 Day: Stent Case
 
Procedural Day +4 Days or Beyond to Discharge Day: Stenting Cases
 
The day after discharge to the observation day of Month 8: 8 months for analysis by time point of stenting
 
Observation day of 8 months to 1 year: 1 year for analysis by time point of stenting
 
Observation day 1 to 2 years after the observation day of 1 year: 2 years for analysis by time point of stented patients
 
Observation day of 2-year observation day to 3-year observation day: 3 years for analysis by time point of stented patients
 
Observation day of the following day of observation in Year 3 to Year 4: 4 years for analysis by time point of stent implantation
 
Observation day of the following day of observation in Year 4 to Year 5: 5 years for analysis by time point of stenting
 
During hospitalization: patients with stents
 
Until 8 months: Stent implantation
 
Until 1 year: Stent implantation
 
Until 2 years: Cases of stenting
 
Until 3 years: Cases of stenting
 
Until 4 years: Cases of stenting
 
Until the end of the survey: patients undergoing stent placement
 
Overall post-procedure: stenting cases


Items	Calculation method, etc.
Confidence interval for the incidence	
Accurate confidence intervals based on Clopper-Pearson method will be calculated.
 $\pi_L = \frac{v_2}{v_2 + v_1 F_{\alpha/2}[v_1, v_2]} \quad v_1 = 2(n - x + 1), v_2 = 2x$ $\pi_U = \frac{v_1 F_{\alpha/2}[v_1, v_2]}{v_2 + v_1 F_{\alpha/2}[v_1, v_2]} \quad v_1 = 2(x + 1), v_2 = 2(n - x)$
Age (years)	The actual age at the date of the procedure (date of registration) is calculated from the date of birth (date is read in one day).
Body Mass Index	Calculated from weight (kg) and height (cm). Body Mass Index = Weight (kg)/ (Height (cm)/100) ²
Acceptable range on the observation day	
Observation day of 8 months: ± 30 days 8 months after the procedure day Observation day 1 year: ± 30 days after the procedure day Observation date of 2 years: ± 30 days 2 years after the procedure date Observation day 3 years: ± 30 days 3 years after the procedure date Observation day in Year 4: ± 30 days 4 years after the procedure date Observation day in 5 years: ± 30 days 5 years after the procedure date
 
However, if it can be confirmed that there is no problem with the data quality, it should be adopted as the data at the time according to the time of the questionnaire, even if it is outside the range.

4. Statistical Analysis Content

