5. OBSERVATION ITEMS AT EACH TIME POINT

5.1 Baseline Information

1) Patient Basic Information

- Index Procedure Date (Date of Registration)
- Birth year and month
- Implant of XIENCE PRIME STENT (Only basic information, non-implant stent form and device deficiency form must be completed in the case all PRIME stents are failed to implant)
- Gender
- Height
- Weight
- Admission and Discharge dates

2) Cardiac Status at the Index Procedure and Cardiac History

- Cardiac Status (Symptom of ischemia) at the Index Procedure
- History of Myocardial Infarction
- Previous CABG
- Previous PCI

3) Risk Factors

- Family History of Premature Coronary Artery Disease

Confidential and Proprietary

Do not distribute or reproduce without the prior written permission of Abbott Vascular Inc.

- Smoking History
- Hypertension
- Dyslipidemia
- Diabetic Mellitus
- Renal Disease
- History of Stroke
- History of Major Bleeding
- Unstable Arrhythmia
- Chronic Anticoagulant Therapy

4) Pre-Procedure ECG**5) Pre-Procedure Cardiac Enzyme and Creatinine**

- Cardiac Enzyme
 - CK
 - CK-MB (If MI is suspected then must be measured per site standard practice)
- Serum Creatinine

6) Pre-Procedure Antiplatelet

- Aspirin
- Clopidogrel
- Ticlopidine
- Other anti-platelet medications
-

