4.1.7. Risk Factors and History

The proportion and confidence interval of relevant cases will be calculated for the risk factors and medical history specified below.

Table 6 Risk Factors and History

- Analysis set: Stent implantation cases (newly enrolled patients)

Items [] indicating Breakdown

No	Item name
1	LVEF < 30%
2	History of myocardial infarction
3	History of CABG
4	History of PCI
5	Family History of Juvenile Coronary Artery Disease
6	Current smoking or cessation within the past month
7	Hypertension [requiring pharmacotherapy, not requiring pharmacotherapy]
8	Dyslipidemia [requiring pharmacotherapy, not requiring pharmacotherapy]
9	Renal failure (kidney disease) History [introdialytic, end-stage renal failure (eGFR < 30 mL/min/1.73m ²), chronic kidney disease (eGFR < 60 mL/min/1.73m ²)]
10	History of stroke
11	History of serious bleeding

No	Item name
12	History of unstable arrhythmia
13	Anticoagulant therapy

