4.2.5. Bifurcation lesion information

The proportion and confidence interval of relevant cases will be calculated by product for the branching lesion information specified below.

Table 12. Branch lesion information

- Analysis set: Stent implantation cases (newly enrolled patients)

Items

No	Item name
1	Branched-lesion True
2	Branched-lesion False
3	Divergent lesion type unknown
4	Detailed retention below

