4.2.8. Success rate

Success rates and confidence intervals will be calculated by product for per-device placement (XP_SV only), per-lesion procedure and per-patient XP_SV placement.

No	Items	Analysis set
1	Successful placement per device (XP_SV only)	Number of devices used by the study population cases
2	Successful procedure for each lesion	Number of lesions in the subject cases (only those for which lesion information is collected)
3	Successful XP_SV placement per patient	Number of subjects surveyed

Table 15. Success rate

- Analysis set: Surveyed patients (newly enrolled patients)

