4.5.2. List of Incidence of Failures and Infectious Diseases by Patient Background

The number of patients, the number of patients with malfunctions and infections, and the incidence of malfunctions and infections will be calculated according to patient characteristics.

List of Incidence of Failures and Infectious Diseases by Patient Background

- Analysis set: Stent implantation cases (newly enrolled patients)

Patient characteristics: [] indicating Breakdown

No	Item name
1	Acute myocardial infarction (yes/no) [ST-segment elevation myocardial infarction, non-ST-segment elevation myocardial infarction]
2	Unstable angina pectoris (with or without) [Blanwald classification: Class I to Class III]
3	Stable angina pectoris (with or without) [CCS angina classification: Class I-IV]
4	Asymptomatic ischemia (with or without)
5	Old myocardial infarction (no evidence of ischemia) (yes/no)
6	Coronary artery stenosis (no evidence of ischemia) (yes/no)
7	Age (<75 years, ≥ 75 years)
8	Sex at birth (male, female)
9	Height (< 160cm, > 160cm, < 170cm, > 170cm)
10	Body weight (< 60kg, ≥ 60 kg, < 70kg, and ≥ 70 kg)
11	Body Mass Index (less than 18.5kg/m ² , greater than 18.5kg/m ² , less than 25kg/m ² , greater than 25kg/m ² , less than 30kg/m ² , greater than or equal to 30kg/m ² , less than 35kg/m ² , greater than or equal to 35kg/m ² , less than or equal to 40kg/m ² , greater than or equal to 40kg/m ²)
12	LVEF < 30% (< 30, > 30)
13	History of myocardial infarction (yes/no)
14	History of CABG (with or without)
15	Past PCI (Yes, No)

No	Item name
16	Family history of juvenile coronary artery disease (yes/no)
17	If you are currently smoking or quit smoking within the past month (yes/no).
18	Hypertension (yes/no) [requiring pharmacotherapy, not requiring pharmacotherapy]
19	Dyslipidemia (yes/no) [requiring pharmacotherapy, not requiring pharmacotherapy]
20	Renal failure (Kidney disease) History (yes/no) [On dialysis, end-stage renal failure (eGFR < 30 mL/min/1.73m ²), chronic kidney disease (eGFR < 60 mL/min/1.73m ²)]
21	History of stroke (yes/no)
22	History of serious bleeding (with or without)
23	History of unstable arrhythmia (present or absent)
24	Anticoagulant therapy (continuous administration, no continued administration)
25	History of diabetes mellitus (with or without) [Type 1 diabetes mellitus, Type 2 diabetes mellitus]
26	History of diabetes mellitus requiring medical care (with or without) [insulin therapy, oral antidiabetic drug therapy]

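### Keeping missing values in the denominator (SAP 3.2) turns rates defined by a measured cut-off, such as LVEF < 30% and the BMI bands, into lower bounds, with no planned count of missing values

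*SAP*

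**What the plan says.** The entry for incidence summaries in SAP 3.2 sets the output for a proportion: "Incidence rates (%), number of events (molecules), number of populations analyzed (denominators) and 95% confidence intervals of frequencies are calculated". It then adds that "cases in which the relevant variable is a missing value are also included in the population of the incidence calculation". The same entry fixes populations for sections 4.3 (antiplatelet therapy) and 4.4 (adverse events). It makes no exception for the baseline tables in 4.1.

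For Table 6, SAP 4.1.7 says: "The proportion and confidence interval of relevant cases will be calculated for the risk factors and medical history specified below". Its first item is LVEF below 30%, and the table has no row for patients whose LVEF was not measured. SAP 4.1.6 (Table 5) reports BMI both as a continuous summary and in six bands, again with no unknown row. By contrast, Table 12 in SAP 4.2.5 has a row "Divergent lesion type unknown".

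SAP 4.5.2 uses LVEF as a background factor with two levels, "LVEF < 30% (< 30, > 30", and no level for missing. The protocol lists LVEF among the procedure items (5.2) and height and weight among the baseline items (5.1), without stating that they must be obtained. Neither document describes imputation or a sensitivity analysis for missing baseline values.

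**The concern.** For a cut-off on a measurement, not measured and measured but not below the cut-off are different states. The rule merges them. A blank LVEF lowers the reported share with severe left ventricular dysfunction exactly as a normal LVEF would, and the exact interval treats it as an observed negative.

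A reader of Table 6 could not see or undo this, because LVEF appears there only as a proportion and no number measured is planned. For BMI the number measured could be read from the sample size of the continuous summary. Even so, the six bands would add to less than 100% without explanation if any height or weight were missing.

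Missing values are plausible because the survey has no particular inclusion or exclusion criteria and treatment follows each site's standard practice. At stake is how accurately the tables describe the population to which the event rates apply. Items with different missing shares would also be understated by different amounts within one table.

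**Working it through.** **The plan's own precision figure.** Protocol 2.3 and SAP 1.3 give a 95% CI half-width of 4.2% for a MACE rate of 15% with 300 patients. Clopper-Pearson at 45/300 gives 11.16% to 19.55%. The half-width is (19.55 − 11.16)/2 = 4.2 points, and 4.2/15 = 28%. The figure reproduces and does not depend on the missing-value rule.

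**Inputs.** N = 300 is the registration target; the actual denominator of Tables 5 and 6 is newly enrolled stented patients, whose number may differ. Clopper-Pearson is the SAP 3.2 method. The documents give no missing share and no rate of LVEF < 30%. Both are therefore assumed: 10%, 20% and 40% missing, and about 5% or 10% below the cut-off among those measured.

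**Formulas.** Let x be the number observed below the cut-off, m the number not measured, and u the unknown number of those m who are below it (0 ≤ u ≤ m).

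- SAP rate = x/N
- Measured-only rate = x/(N − m)
- Full-data rate = (x + u)/N, which lies between x/N and (x + m)/N

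Because u ≥ 0, the SAP rate can never exceed the full-data rate, and equals it only when u = 0. If missingness is unrelated to the value, the expected SAP rate is the true rate × (1 − m/N). A true 5% would then be reported on average as 4.5%, 4.0% or 3.0% at 10%, 20% or 40% missing.

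**Results** (whole-patient counts, 95% CI in brackets):

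| Missing m | x | SAP rate, x/300 | Measured only, x/(300 − m) | Full-data range |
|---|---|---|---|---|
| 30 (10%) | 14 | 4.7% (2.6–7.7) | 14/270 = 5.2% (2.9–8.5) | 4.7–14.7% |
| 60 (20%) | 12 | 4.0% (2.1–6.9) | 12/240 = 5.0% (2.6–8.6) | 4.0–24.0% |
| 120 (40%) | 9 | 3.0% (1.4–5.6) | 9/180 = 5.0% (2.3–9.3) | 3.0–43.0% |
| 30 (10%) | 27 | 9.0% (6.0–12.8) | 27/270 = 10.0% (6.7–14.2) | 9.0–19.0% |
| 60 (20%) | 24 | 8.0% (5.2–11.7) | 24/240 = 10.0% (6.5–14.5) | 8.0–28.0% |
| 120 (40%) | 18 | 6.0% (3.6–9.3) | 18/180 = 10.0% (6.0–15.3) | 6.0–46.0% |

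At 20% missing with 12 cases, the SAP interval is 6.9 − 2.1 = 4.8 points wide, against 8.6 − 2.6 = 6.0 for the measured patients. In this grid the SAP interval excludes the measured-only rate only in the last row. The last column shows how much the rule leaves unsaid: the SAP rate is always its left end.

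**The case against.** **No missing share is given.** With complete data there is no distortion, and the documents do not show that values will be missing. This stands. The direction is certain, but the size is unknown.

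**The measured-only rate is not automatically the truth.** If sites measure LVEF mainly when dysfunction is suspected, the measured-only rate is too high and the SAP rate may be closer. This also stands. The contrast of 4.0% with 5.0% holds only if missingness is unrelated to the value, so changing the denominator alone is not enough.

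**The tables are descriptive.** Protocol 6.1 names stent thrombosis and antiplatelet-related adverse events as the important items, and neither rate is altered. This limits the weight of the point.

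Three stronger readings are tempting but unsupported.

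- *An unmeasured creatinine counts as normal renal function.* The category "chronic kidney disease (eGFR < 60 mL/min/1.73m ²") is part of the breakdown of a history item in Table 6. Protocol 5.1 lists renal disease as a risk factor, separately from "Serum Creatinine" among the laboratory values. SAP 3.2 gives formulas for age and BMI but none for eGFR. The bands may be site-recorded categories. A blank renal-history entry would still count as no, but the documents do not tie that to a missing creatinine.
- *The SAP contradicts its own rule in Table 15.* Row 2 of SAP 4.2.8 limits the lesion denominator to "only those for which lesion information is collected". That table covers all surveyed patients, including those in whom the stent could not be placed, and Protocol 2.2 and 5.1 require only limited forms for them. Lesion data not collected by design explain the restriction.
- *Every proportion is affected alike.* For presence/absence items such as complex-lesion features or lesion preparation, a blank may simply mean absent. Dropping blanks there would push proportions towards 100%.

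**Conclusion.** The point holds for items defined by a cut-off on a measured value: LVEF < 30% in Table 6 and the BMI bands in Table 5. As written, SAP 3.2 scores an unmeasured patient as not meeting the cut-off. Whenever values are missing, it yields a lower bound presented as an estimate, with an interval based on more patients than were measured.

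If missingness is unrelated to the value, the relative understatement equals the missing share. At an assumed 20% missing, that is one percentage point on a rate of 5% and two points on a rate of 10%. These prevalences and missing shares are illustrations, not figures from the documents. Without the assumption about missingness, only the direction is established.

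The consequence is confined to the description of the population. It is worth correcting because the effect on LVEF cannot be seen in the planned output and the remedy is simple.

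**What to change.** In SAP 3.2, limit the missing-value rule and add, for items based on a measured value (LVEF < 30%, BMI bands):

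- the denominator is the number of cases with a recorded value;
- the number missing is shown beside it;
- the range is given from none to all of the missing cases meeting the cut-off, that is x/N to (x + m)/N.

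In the SAP 4.5.2 split by LVEF, show the number missing as well. For the renal-history item, state whether the eGFR bands are recorded by the site or derived from creatinine; if derived, treat them in the same way.

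Leave presence/absence items where a blank means absent, and all tables in 4.3 and 4.4, as they are.

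The cost is SAP wording and table programming. Denominators will vary by item, some intervals will be slightly wider, and the none-to-all range will be wide where many values are missing.

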2.2 Enrollment Method

- Patient informed consent is required for registration of this PMS In cases where patient informed consent (or providing some type of information) is required for PMS per the participating site policy, the Sponsor will cooperate as needed.
- If it is known at the time of index procedure that the patient is not able to return for the 8-month follow-up visit for angiogram and for the 1-year clinical follow-up, then the patient should not be registered in the PMS.
- Patients who are treated (stent delivery system inserted into the body) by XIENCE PRIME SV will be registered (including provisional stenting for side branch treatment but excluding bail-out only use)
 - The observations will be compiled on a per-patient basis even if multiple stents are implanted during the index procedure.

- A patient whose side-branch is treated by XIENCE PRIME SV can be registered. In such a case, main vessel should be treated by XIENCE PRIME.
- A patient who are treated by other DES for planned stent and XIENCE PRIME SV for bail-out purpose cannot be registered.
- Additional revascularization procedures as a part of AE treatment and planned staged procedures will not be considered as another registration, or adverse events.
- A patient who is treated, but failed to be implanted by XIENCE PRIME SV and finally treated by other devices only (No XIENCE PRIME SV are implanted) must also be registered. In such a case, only the stent information, device deficiency information and reportable adverse events related to the PRIME stent, if any, are required to be captured. Follow-up of the patient who does not receive any XIENCE PRIME SV stent is not required.
- A patient may have another lesion(s) that may be treated by larger diameter stent(s). In such a case, treatment by XIENCE PRIME is preferable. Lesion(s) treated by other than XIENCE PRIME is not considered as the target lesion.

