2.1. Analysis population definitions

No	Definition name	Definition Content
1	Survey period	March 7, 2013 - December 31, 2019
2	Date of data lock (snapshot)	Data lock (snapshot) dates for annual reports are as follows 1st: September 5, 2013 2nd: September 5, 2014 3rd: September 5, 2015 4th: September 5, 2016 5th: September 5, 2017 6th: September 5, 2018 7th: September 5, 2019 Reexamination: September 5, 2019 Subjects with fixed CRFs by the time of data lock.
3	CRF-collected subjects	Subjects whose CRFs were fixed
4	Subjects who are out of the survey	The cases who were treated with out-of survey stent, among CRF-collected subjects in newly enrolled patients.
5	Subjects to be investigated	The cases excluding subjects who are out of the survey among CRF-collected subjects.
6	Non-stent implanted subjects	Among the subjects studied, the cases in which the stent to be investigated could not be placed.
7	Stenting subjects	Among the investigated subjects in newly enrolled patients, the cases who were treated with investigated stent Investigated subjects transitioning from the pre-market study.
8	Newly enrolled patients	Patients enrolled for the first time in this survey.
9	Patients transitioning from the study	Patients who participated in the Clinical Assessment of AVJ-09-385 Coronary Stenting in Japanese Subjects in AVJ-09-385 Coronary Stenting Trial.

No	Definition name	Definition Content

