4.4. Adverse Events

4.4.1. Adverse events (composite endpoint)

For adverse events (composite endpoint), incidence rates will be calculated by product for each time of onset.

No	Time of onset
1	Procedural day + 3 days from procedure date
2	Procedural Day + Day 4 or later to discharge date
3	Observation day of the day after discharge to Month 8
4	Observation day of Month 8 to Observation day of Year 1
5	Observation day of 1 year to the following day of 2 years
6	Observation day of the following day of Year 2 to Observation day of Year 3
7	Observation day of Year 3 to Year 4
8	Observation day following the observation day of Year 4 to the observation day of Year 5
9	During hospitalization
10	Up to 8 months
11	Until one year
12	Until 2 years
13	Up to 3 years
14	Up to 4 years
15	Until the end of the survey
16	Entire post-procedure

Table 18. Adverse events (composite endpoint, by time of onset)

- Analysis set: Stent implantation cases (newly enrolled patients)

Items [] indicating Breakdown

No	Item name
1	Target Lesion Failure [TLR Based on Cardiac Death, Myocardial Infarction Associated with Target Vessels, and Ischemic Findings].
2	Death + myocardial infarction + revascularization [death, myocardial infarction, revascularization]
3	Target vessel failure [cardiac death, myocardial infarction, TLR based on ischemic findings, TVR (non-TLR) based on ischemic findings, TVR (TLR or TVR (non-TLR)) based on ischemic findings].
4	Major adverse cardiac events (cardiac death, total myocardial infarction, TLR based on ischemic findings)
5	Death or myocardial infarction
6	Cardiac death or myocardial infarction
7	Myocardial infarction related to cardiac death or target vessel

Determination of myocardial infarction is based on the WHO (SPIRIT III) definitions

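### Acute event rates cover only patients with an implanted SV stent, so stent-related events after a complete delivery failure enter no rate in Tables 18 and 19

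*SAP*

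**What the plan says.** Protocol 2.2 registers a patient once the delivery system has entered the body. A patient who ends up with other devices only must still be registered. For that patient, besides stent information, "device deficiency information and reportable adverse events related to the PRIME stent, if any, are required to be captured", and no follow-up is required. Protocol 5.1 lists the forms for a complete failure as basic information, the non-implant stent form and the device deficiency form. It names no adverse event form.

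SAP 2.1 puts these patients in definition 6, "the cases in which the stent to be investigated could not be placed", apart from the stenting subjects of definition 7.

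SAP 3.2 then fixes the populations for the adverse event tables:

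- Row 1: "Procedural Day + 3 Day: Stent Case"
- Row 2: "Procedural Day +4 Days or Beyond to Discharge Day: Stenting Cases"
- Row 9: "During hospitalization: patients with stents"
- Cumulative rows, ending with "Overall post-procedure: stenting cases"

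Tables 18 and 19 (SAP 4.4.1 and 4.4.2) repeat the restriction: "Analysis set: Stent implantation cases (newly enrolled patients)". Table 15 on success rates (SAP 4.2.8) uses the wider set: "Analysis set: Surveyed patients (newly enrolled patients)".

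The malfunction list (4.5.1) and the serious adverse event list (4.5.3) name stented cases as their analysis set, but divide by the number of patients surveyed.

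**The concern.** Rows 1, 2 and 9 cover the procedure and the stay that follows it, yet membership of their population depends on how the procedure ended. Suppose a patient has a stent-related myocardial infarction during a failed delivery, and the event is recorded as Protocol 2.2 asks. It is then in neither the numerator nor the denominator of any rate in Tables 18 and 19. The lack of follow-up explains the restriction for periods after discharge, but not for the hospital stay.

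The survey's stated purpose is to assure the safety of the device, and harm during an attempt that fails is part of that. The two lists in SAP 4.5 do not clearly fill the gap. If their stated analysis set governs the numerator, they combine events in stented patients with a denominator of all surveyed patients, and the result is the rate of neither group.

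**Working it through.** **The plan's own figure.** Protocol 2.3 and SAP 1.3 give a 95% half-width of 4.2% for a 15% MACE rate in 300 patients. Clopper-Pearson (the method in SAP 3.2) for 45/300 gives 11.16% to 19.55%. The half-width is 4.198 points, or 28.0% of 15%. The figure reproduces and is unaffected by this point.

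**Which patients are lost.** Only complete failures. A patient with one failed and one implanted SV stent remains a stented case.

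**Formula.** Let f be the share of attempts that fail completely, s the acute event rate in stented patients, and r the rate in failures. Then

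all-attempted rate = (1 - f) × s + f × r, and shift = f × (r - s).

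The shift is positive only if r exceeds s.

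**Inputs.** N = 300 is from Protocol 2.3. The documents give none of f, s or r, so these are assumptions: 6 failures (f = 2%), 6 in-hospital events in 294 stented patients (s = 6/294 = 2.04%), and r from 0% to 50%.

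| r | expected events in 6 failures | all-attempted rate | shift (points) |
|---|---|---|---|
| 0% | 0 | 6/300 = 2.00% | -0.04 |
| 10% | 0.6 | 6.6/300 = 2.20% | +0.16 |
| 20% | 1.2 | 7.2/300 = 2.40% | +0.36 |
| 33.3% | 2 | 8/300 = 2.67% | +0.63 |
| 50% | 3 | 9/300 = 3.00% | +0.96 |

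**Against sampling error.** The Clopper-Pearson interval for 6/294 is 0.75% to 4.39%. With one event among the failures, 7/300 = 2.33% (0.94% to 4.75%). With two, 8/300 = 2.67% (1.16% to 5.19%). The shifts lie well inside the intervals, although two events raise the estimate by 0.63/2.04 = 31% in relative terms.

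**Wider grid.** With 3, 6 or 15 failures, 3, 6 or 12 events in stented patients, and r from 0% to 50%, the extremes are:

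- Lowest: 12/285 = 4.21% against 12/300 = 4.00%, a shift of -0.21.
- Highest: 3/285 = 1.05% against (3 + 7.5)/300 = 3.50%, a shift of +2.45.

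**What a plain change of denominator would do.** Two features of the data stand in the way.

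- Events unrelated to the PRIME stent need not be captured in failures. If two of the six failures had an event and neither was captured, the all-attempted figure would read 6/300 = 2.00%, below the planned 2.04%, when the true value is 2.67%.
- Under Protocol 2.2 and 5.2, a lesion treated only by other devices is not a target lesion. Failed patients would generally contribute zero to TLR by definition. Six extra patients in the denominator would multiply a TLR rate by 294/300 = 0.98 and add no information.

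**The case against.** The strongest reply is that Tables 18 and 19 state their population and are correct for it. An implant-based event table is a legitimate summary, and a per-patient placement success rate has to use all attempts, because on stented cases it would be 100% by construction. The wider set in Table 15 is therefore no contradiction. Failures are also not hidden: SAP 4.1.1 counts them and gives their case numbers, and the listing in 4.7.1 covers all collected cases. The survey is descriptive, and one of its two important evaluation items in Protocol 6.1, stent thrombosis, cannot concern an SV stent that was never placed.

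All of this stands. It does not answer the narrower point: the protocol asks for certain acute events to be captured, and no rate in Tables 18 and 19 uses them. A count or a case listing is not an event rate.

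Definition 7 could be read to include failures, since it speaks of patients treated with the stent and Protocol 2.2 counts insertion of the delivery system as treatment. The separate definition 6 and the table label make that reading unlikely.

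A reader might go further and infer that the in-hospital rates are biased low, or that rows 1, 2 and 9 should simply move to all attempted patients. The documents support neither. The first needs a higher acute event rate in failures, which is plausible but not documented. The second would add patients with incomplete event capture and generally no target lesion, and could lower the rates.

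**Conclusion.** The point holds as an omission in reporting, not as a demonstrated bias. Reportable stent-related events in registered patients with a complete delivery failure enter no rate in Tables 18 and 19, whether acute or cumulative. The stented-only rates are valid for implanted cases and should not be read as acute safety in all patients in whom the device was attempted.

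The size cannot be computed from the documents. At 2% failures and about 2% events in stented patients, the difference runs from -0.04 to +0.96 points for assumed event rates of 0% to 50% in failures. It exceeds 1 point only where failures are frequent and carry high event rates. The mismatch between analysis set and denominator in SAP 4.5.1 and 4.5.3, and the difference between Protocol 2.2 and 5.1 over the adverse event form, can be read directly from the text and need no assumption.

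**What to change.** - Keep Tables 18 and 19 on stented cases, and state in SAP 3.2 that both the acute and the cumulative rows exclude complete delivery failures.
- Add a supplementary table for the period from procedure to discharge, in newly enrolled non-stent-implanted subjects (definition 6). Give their number and the captured reportable events: death, MI, revascularization and other PRIME-related events.
- Beside the stented-only in-hospital figure, give one for newly enrolled subjects to be investigated (definition 5), for death and MI only. Label it a lower bound, because only PRIME-related events are required in failures. Do not compute TLR, TLF or other target-lesion composites for patients without a target lesion.
- In SAP 4.5.1 and 4.5.3, make the analysis set match the surveyed-patient denominator, so that events in failed deliveries are counted in the numerator too.
- Reconcile Protocol 2.2 with 5.1 on whether the adverse event form is completed for failed implants. If forms have already been collected, report which ones were.

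The cost is some SAP wording, one small table and one extra figure each for death and MI, using events that Protocol 2.2 already requires. The acute figure may become slightly less favourable, and with only a handful of failures it will be imprecise, so counts should be shown with any percentage.
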